8.3 Statistical Considerations

8.3.1 Statistical Analysis Plan

A detailed analysis plan will be finalised prior to database lock, below is a brief outline.

8.3.2 Interim Analyses

There are no planned interim analyses.

8.3.3 Statistical Methods – Outcomes

The primary analyses will be a generalised mixed model with identity link and Gaussian / mixed error structures, accounting for baseline scores using a repeated measures framework. There will be two observations for each participant, the baseline and final outcome scores. These will be linked within a participant using a random intercept term. The model will be parameterised to identify baseline and post randomisation observation as one parameter, and random allocation as the second parameter. For the latter, all baseline measures will be coded as no intervention, and the post randomisation values will be classified as active or control. We will not make adjustments for repeated testing but will discuss the possibility that type 1 errors would have increased in the discussion.

We will employ a treatment policy estimand in the primary analysis with inclusion defined as that population of participants who were randomised.

8.3.4 Additional Analyses

Secondary analyses will choose the appropriate analogous generalised mixed model, for the outcome and account for the baseline measurement of the outcome. We will describe randomised groups at baseline. Summary statistics for continuous variables will be mean, median, SD, lower quartile, upper quartile and reported appropriately according to distribution. Summary statistics for binary and categorical variables will be n (%).

We will carry out supportive analyses including the minimisation variables as explanatory variables.

We will carry out, if indicated, a threshold analysis of the primary outcome where missing values in the control group are assigned the best possible outcome values and missing values in the intervention group are assigned the worst possible outcome values to assess the stability of the primary outcome to missingness.

In addition, we will carry out these additional analyses:

Provide the point estimates and standard errors for (1) parental depression (PHQ-8), (2) parental anxiety (GAD-7) and (3) household income. We will also carry out exploratory subgroup analyses by income and by IMD quintile group.

9 Economic Evaluation (WP2)

The aim of WP2 is to apply a novel longitudinal individual-level microsimulation modelling approach to understand how improvements in short-term family income and parental mental health will impact children's long-term health, economic, social, and wellbeing outcomes.

Research questions (RQ):

- RQ1. Do increases in family income and improvements in parental mental health during infancy lead to improved long-term health, economic, social, and wellbeing outcomes for children over the lifecourse?
- RQ2. Will referral to a co-located WBA in LBTH be cost-effective in the long-term, compared with no referral to a co-located WBA?
- RQ3. Would national roll-out of co-located money advice and health services across the whole of England be cost-effective and reduce inequalities in the long-term?

We will conduct two model-based economic evaluations, one local and one national, using a lifecourse microsimulation model called "LifeSim¹⁷":

1. **Local model-based economic evaluation** – a long-term cost-effectiveness analysis of referral to co-located Welfare and Benefits Advice (WBA) in London Borough of Tower Hamlets (LBTH), compared with no referral to co-located WBA (RQ1, RQ2).
2. **National model-based economic evaluation** – a long-term distributional cost-effectiveness analysis of full national implementation of co-located WBA in England, compared with no co-located WBA in England (RQ3).

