5.1 Outcomes

5.1.1 Primary Outcome(s)

Difference in depression (PHQ-8¹¹) scores at 6 months' follow-up in the intervention arm compared with the control arm accounting for baseline values and adjusted for stratification variables (if any). The outcome will be examined to ensure that it meets the assumptions for regression analyses and transformed, if necessary, to an appropriate scale so that the resultant distribution approaches normality.

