8.1 Sample Size

We make the following assumptions:

- I. We take the Minimum Clinically Important Difference (MCID) in PHQ-8¹¹ scores to be half of the usual value of 3. We have chosen this conservative estimate because the population at risk in this study is not known to have a high prevalence of depressive illness (unlike the other environments in which the PHQ-8 has been validated). Additionally, we are not convinced that this population, which encompasses a high proportion of migrants and people of minority ethnicity, will volunteer symptoms of a depressive disorder because of cultural stigma against mental illness. Further, those participants who experience symptoms of low mood may report different symptoms from those elicited on the PHQ scale due to cultural differences in the way they experience low mood. We therefore do not think the PHQ is an appropriately sensitive instrument in this environment and have estimated the sample size with a conservative estimate of the MCID.
- II. We have provided a conservative estimate of the correlation between baseline and follow-up values. This means that the study may be overpowered.
- III. We assume a standard deviation of 7.25 for the change score (which derives from the Born in Bradford study)¹⁶.
- IV. This is a very experienced research team which has conducted substantial research in this area. We have consulted extensively with our PPIE partners, and they do not think that we will encounter high dropout rates. We anticipate that we will have an approximate dropout rate of 10% but are prepared for a 20% dropout rate in our sample size calculations.
- V. We have used the ANCOVA method to calculate the sample size. This method results in a smaller sample size (if we account for baseline adjustment for PHQ-8 scores in the final analysis of the effect of the intervention) than that which would obtain otherwise.

We estimate that we will be able to detect a difference of 1.5 units in the PHQ-8 scale between the two arms with a two-sided alpha of 5% and with 90% power (assuming a nominal correlation of 0.25 between baseline and follow-up scores, a standard deviation of the change score of 7.25 and an anticipated 20% drop-out rate) with a sample size of 1153 participants.

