8.2 Assignment of Intervention

8.2.1 Randomisation Procedures

An independent, concealed, online randomisation service provider (www.sealedenvelope.com) will be used to divide participants equally into the two trial groups.

We will perform individual participant randomisation using stratification factors, detailed in the prespecified SAP, to attempt to balance allocation to both study arms for these variables. We will use a biased coin technique to ensure that the groups are approximately equal but still retaining some component of randomness in the allocation. Randomisation will be performed either by CCTU/UCL Researchers or by a delegated entity via Sealed Envelope (who will use industry standard validated randomisation and/or minimisation algorithms to achieve the aim of 1:1 allocation ratio with the 70% biased coin element of randomness). The Trial Statisticians conducting the trial analyses and involved in the conduct of the study will be blinded to trial group allocation until the end of the trial when data analysis and unblinding occurs.

Following the Baseline visit, the UCL Researcher or delegate will enter minimisation factors as well as the necessary data to re-confirm participant eligibility on the SealedEnvelope.com secure online system and then allocate the appropriate PIN to the participant.

Delegated staff (at CCTU/UCL Researchers or appropriate designee) will be provided with a secure login to the SealedEnvelope.com Website, according to their role in the trial. The randomisation result will be shown directly online as the intervention allocation, with an email confirmation sent to the user and to the CCTU trial team. If allocated to the intervention group, the UCL Researcher will book a WBA appointment and provide details to the participant.

Randomisation will be considered completed after allocation has been generated from the randomisation system.

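### The protocol states two primary analyses: the outcome definition adjusts for the balancing factors, but the primary model omits them and moves them to a supportive analysis

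*Protocol*

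**What the plan says.** **Outcome definition.** Section 5.1.1, like the trial summary table, defines the primary comparison of 6-month PHQ-8 scores as "accounting for baseline values and adjusted for stratification variables (if any"). Section 5.1.2 words household income in the same way. GAD-7, SWEMWBS and EQ-5D-5L are defined there as accounting for baseline values, with no mention of stratification variables.

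**Randomisation.** Section 8.2.1 states: "We will perform individual participant randomisation using stratification factors, detailed in the prespecified SAP". It adds a 70% biased coin and has the researcher enter minimisation factors in the online system. The trial summary table also says that minimisation factors are used.

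**Primary model.** Section 8.3.3 specifies a mixed model with a random intercept linking each participant's two observations. Its fixed part is described thus: "The model will be parameterised to identify baseline and post randomisation observation as one parameter, and random allocation as the second parameter". No balancing factor appears.

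**Place of the factors.** Section 8.3.4: "We will carry out supportive analyses including the minimisation variables as explanatory variables".

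**The concern.** An analysis plan written from this protocol can follow 5.1.1 or it can follow 8.3.3 with 8.3.4, but not both. One makes the factor-adjusted contrast primary; the other makes it supportive.

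The difference has a statistical consequence. Minimisation makes the arms more alike on the chosen factors than simple randomisation would, so the estimated difference varies less from trial to trial. A model without the factors cannot see this. It leaves their variance in the residual and reports a standard error suited to simple randomisation. If the factors predict PHQ-8, confidence intervals are then too wide, type I error falls below 5% and some power is given up. At stake are which result counts as confirmatory and a modest amount of precision.

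**Working it through.** **1. The texts side by side.**

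| Place | Balancing factors in the primary comparison? |
|---|---|
| 5.1.1 and the trial summary table | Yes, if there are any |
| 8.2.1 and the trial summary table | Such factors exist; their names are left to the SAP |
| 8.3.3 | Not among the model terms |
| 8.3.4 | Supportive analyses only |

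**2. The protocol's own sample size.** The inputs are in section 8.1: "detect a difference of 1.5 units in the PHQ-8 scale between the two arms", "with a two-sided alpha of 5% and with 90% power", "We assume a standard deviation of 7.25 for the change score", "assuming a nominal correlation of 0.25 between baseline and follow-up scores", and 20% dropout.

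- Residual SD after baseline adjustment: 7.25 × √(1 − 0.25²) = 7.02.
- Per arm: 2 × [7.02 × (1.960 + 1.282) / 1.5]² = 460.2, so 461 per arm and 922 in total.
- With dropout: 922 / 0.8 = 1152.5, so 1153, as stated.
- Power at 10% dropout: 93.1%, against 93% stated.

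The match requires 7.25 to enter as the SD of the score although it is labelled a change-score SD. That is a separate matter. What counts here is that 1153 makes no allowance for the balancing factors.

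**3. Effect of omitting the factors.** Let R² be the share of follow-up variance beyond baseline that the factors explain. The protocol names no factors, so R² is an assumption. Assume perfect balance and 461 completers per arm.

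- SE reported without the factors: 7.02 × √(2/461) = 0.462.
- SE with the factors, which under perfect balance is also the true SD of the unadjusted estimate: 0.462 × √(1 − R²).
- Type I error without the factors: 2 × [1 − Φ(1.96/√(1 − R²))].
- Power without the factors: Φ((1.5 − 1.96 × 0.462) / SE with factors).
- Power with the factors: Φ(1.5 / SE with factors − 1.96).

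| R² | 95% CI half-width, without / with | Type I error, without | Power, without | Power, with |
|---|---|---|---|---|
| 0 | 0.906 / 0.906 | 5.0% | 90.0% | 90.0% |
| 5% | 0.906 / 0.883 | 4.4% | 90.6% | 91.4% |
| 10% | 0.906 / 0.860 | 3.9% | 91.2% | 92.8% |
| 20% | 0.906 / 0.811 | 2.8% | 92.4% | 95.2% |

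**4. With the 70% biased coin.** A simulation used 5,000 trials per scenario, N = 1153, 20% random dropout, three assumed factors with 8, 2 and 3 levels, and ANCOVA in place of the mixed model. At R² of 5%, 10% and 20%, type I error without the factors was 4.4%, 4.2% and 3.0%; with them it was 4.7% to 5.1%. Power was 90.7%, 91.3% and 92.3% without the factors, and 91.6%, 93.0% and 95.3% with them.

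**5. How plausible the range is.** In a random-intercept model with correlation 0.25, stable between-person variance is 0.25 of the total. Suppose the factors act equally at both times and explain a fraction f of total variance. The residual variance given baseline and factors is (1 − f) − (0.25 − f)²/(1 − f), against 0.9375 without the factors.

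- R² = 5% needs f ≈ 0.0775, which is 31% of the stable variance.
- R² = 10% needs f ≈ 0.1425, which is 57%.
- R² = 20% needs f = 0.25, which is all of it.

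**6. Main effect or interaction with time.** The protocol's own type of model was simulated with 922 complete pairs and one binary factor.

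- Factor acting equally at both times (14.3% of score variance): type I error was 4.1% without the factor, 5.0% with a main effect, and 5.0% with main effect plus interaction. The main effect was enough.
- Factor acting only at follow-up (R² 20%): a main effect alone left type I error at 4.0%; adding the interaction gave 5.2%.

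**The case against.** **The SAP will settle it.** Section 8.3.1 calls the text a brief outline and has the detailed plan finalised before database lock, and the trial statisticians are blinded meanwhile. This limits the scope for a choice driven by the results, and leaving the factor names to the SAP is in order. It does not remove the conflict, because 8.3.4 positively gives the factors a supportive role that 5.1.1 contradicts.

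**The qualifier (if any), or a difference between stratification and minimisation.** Section 8.2.1 uses both words within one description of the allocation, and only one set of balancing variables is described. Such factors exist.

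**The consequence is conservative and may be small.** This stands. No bias arises, type I error is at or below 5%, and with non-prognostic factors nothing changes.

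A reader might go further in four ways that the documents do not support:

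- **That the intervals are too wide as a fact.** The factors are unnamed, so their prognostic value is unknown.
- **That adjustment lifts power from 90% to as much as 95%.** Under the same balance, power without the factors is already 92.4% at R² = 20%. The gains are about 0.8, 1.6 and 2.8 points.
- **That every factor must have an interaction with time.** A time-constant main effect does adjust the contrast when the factor acts equally at both times, and the protocol does not say that any factor acts differently.
- **That three secondary outcomes are defined with no adjustment.** GAD-7, SWEMWBS and EQ-5D-5L are defined as accounting for baseline; only the balancing factors are absent.

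**Conclusion.** The contradiction is firm and rests on the text alone: 5.1.1 and 8.3.3/8.3.4 give different primary analyses of PHQ-8. For income, 5.1.2 asks for the stratification adjustment, while 8.3.4 promises a model analogous to the primary one and mentions only the baseline measurement.

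The statistical cost of the version in 8.3.3 is conditional. It depends on an assumed R² for unnamed factors. At 5% to 10%, the reported standard error is about 3% to 5% too large under perfect balance (1/√0.95 = 1.026; 1/√0.90 = 1.054), and adjustment gains roughly 1 to 2 points of power. The figures at 20% would require factors that capture all stable variation in PHQ-8, or that predict follow-up much better than baseline. Neither the treatment estimate nor the planned 90% power is at risk. The correction is still worth making, since it settles which analysis is primary and uses data already held.

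**What to change.** - **8.3.3:** include all minimisation/stratification factors as fixed effects in the primary model. A factor-by-time interaction is a safe general form, needed only if a factor's effect differs between baseline and 6 months. The SAP can name the factors and settle this.
- **5.1.2 and 8.3.4:** use the same set of factors for income, GAD-7, SWEMWBS and EQ-5D-5L.
- **5.1.1, 5.1.2 and the trial summary table:** delete the qualifier (if any).
- **Throughout:** use one term for the factors.
- **8.3.4:** make the model without the factors the supportive analysis.

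The cost is a wording change in the protocol, carried into the SAP before database lock. The factors are entered at randomisation, so no new data are needed, and the sample size stays at 1153.

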ICH	International Conference on Harmonisation
ICF	Informed Consent Form
IRAS	Integrated Research Application System
ISF	Investigator Site File
ISRCTN	International Standard Randomised Controlled Trial Number
LBTH	London Borough of Tower Hamlets
LBN	London Borough of Newham
MCS	Millenium Cohort Study

NHS	National Health Service
NIHR	National Institute for Health and Care Research
OHID	Office for Health Improvements and Disparities
PHQ-8	Patient Health Questionnaire-8
PIN	Participant Identification Number
PIS	Participant Information Sheet
PPI	Patient and Public Involvement
QA	Quality Assurance
QALY	Quality Adjusted Life Years
QC	Quality Control
QMMP	Quality Management and Monitoring Plan
R&D	Research and Development
REC	Research Ethics Committee
SAE	Serious Adverse Event
SAP	Statistical Analysis Plan
SOP	Standard Operating Procedure
SWEMWBS	Short Warwick–Edinburgh Mental Well-Being Scale
TMF	Trial Master File
TMG	Trial Management Group
ToR	Terms of Reference
TSC	Trial Steering Committee
UCL	University College London
UKPRP	UK Prevention Research Partnership
WBA	Welfare and Benefits Advisor
WP	Work Package

Glossary

Term	Definition
EQ-5D-5L	EuroQol-5 Dimension 5-level; a 5-item instrument measuring health-related quality of life.
GAD-7	General Anxiety Disorder-7; a 7-item instrument measuring anxiety with a 4-item scale.
LifeSim	A computer programme for childhood policy analysis that models developmental, economic, social and health outcomes from birth to death.
PHQ-8	Patient Health Questionnaire Depression Scale; an 8-item instrument measuring depression with a 4-item scale.
Subjective Financial situation ¹⁵	A single item measure on a 5-level scale, 'living comfortably' to 'finding it very difficult'.
SWEMWBS	Short Warwick-Edinburgh Mental Wellbeing Scale; a 7-item self-report measure of mental wellbeing with five response options ('none of the time' to 'all of the time'), to give a total score ranging from 7-35, which is validated for use in multiple languages and contexts.
WELLBY	Wellbeing-adjusted Life Year; a one-point life satisfaction measured on a 0-to-10 Likert scale for one individual for one year.

1 Background

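### The missing-data threshold analysis in Section 8.3.4 is one extreme bound: at the trial's own dropout figures it reverses the 1.5-point target effect, and it locates no threshold

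*Protocol*

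**What the plan says.** Section 8.3.4 of the protocol states: "We will carry out, if indicated, a threshold analysis of the primary outcome". The rule is that "missing values in the control group are assigned the best possible outcome values", while "missing values in the intervention group are assigned the worst possible outcome values to assess the stability of the primary outcome to missingness". So the protocol fixes the imputed values for each arm, the label and the purpose. The section gives no other imputed values and no quantity to be varied.

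Three other places supply the scale of the problem:

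- Section 8.1 sizes the trial to "detect a difference of 1.5 units in the PHQ-8 scale between the two arms", having set the important difference in PHQ-8 "scores to be half of the usual value of 3".
- Section 8.1 anticipates about 10% dropout, but the authors "are prepared for a 20% dropout rate in our sample size calculations".
- The Glossary describes the PHQ-8 as "an 8-item instrument measuring depression with a 4-item scale".

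**The concern.** A threshold, or tipping-point, analysis varies an assumption about the missing scores until the conclusion changes, so that a reader can judge whether that point is believable. The stated rule evaluates one corner of the possible values and stops there. Every missing participant in one arm is assumed free of symptoms, and every missing participant in the other is assumed to have the maximum score.

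On a scale many times wider than the target difference, that corner can overwhelm the observed data at quite low dropout. A finding that is robust to any moderate departure from missing at random would then look fragile, and a reader would learn nothing about moderate departures. This matters here because participants are unblinded, the outcome is self-reported, and Section 8.1 itself expects stigma to affect the reporting of symptoms. Non-response related to arm and to mood is a realistic possibility that deserves an informative check.

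**Working it through.** **Inputs.** Target difference 1.5, usual important difference 3, SD 7.25, correlation 0.25, two-sided 5%, 90% power, dropout 10% and 20%, N = 1153, 1:1 allocation (Sections 8.1 and 8.2.2). Scale width: 8 items × 3 steps = 24 points. The width is not printed; it follows from the Glossary if the four levels are scored as consecutive integers.

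**The plan's own figure first.** ANCOVA SD = 7.25 × √(1 − 0.25²) = 7.02. Per arm: 2 × (7.02 × (1.960 + 1.282) / 1.5)² ≈ 460.2, rounded up to 461, or 922 in total. 922 / 0.8 = 1152.5, giving 1153. Power is 0.901 at 20% dropout and 0.931 at 10%. The sample size and both stated power figures reproduce, so these inputs are read as the authors used them.

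**Effect of the rule.** Let m be the missing fraction in each arm and b the benefit among completers. The difference is intervention minus control, so positive means harm.

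- Difference after imputation = 24m − (1 − m)b
- Benefit needed to reach zero = 24m / (1 − m)
- Missing fraction at which benefit b vanishes = b / (24 + b)

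| Missing per arm | b = 1.5 | b = 3 | Break-even benefit |
|---|---|---|---|
| 5% | 1.2 − 1.425 = −0.225 | 1.2 − 2.85 = −1.65 | 1.26 |
| 10% | 2.4 − 1.35 = +1.05 | 2.4 − 2.7 = −0.30 | 2.67 |
| 20% | 4.8 − 1.2 = +3.60 | 4.8 − 2.4 = +2.40 | 6.0 |

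The target effect loses its sign at m = 1.5 / 25.5 = 5.9%. The pilot criteria in Section 3.3.4 rate 75% retention as green; at 25% missing the break-even is 24 × 0.25 / 0.75 = 8 points.

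**Precision.** The protocol gives no follow-up mean, so I assumed a control mean of 4 to 8 and an SD of 4 to 7.25. For the 1.5-point target, z after imputation is +6.8 to +9.4 at 20% missing and +2.1 to +3.2 at 10%: significant harm in both cases. A 3-point benefit gives z of +4.4 to +6.0 at 20%, and −0.6 to −0.9 at 10%. With a control mean of 6, the target effect stays significantly favourable only up to about 2.4% missing (SD 7.25) to 3.7% missing (SD 4).

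**Simulation check.** Baseline-adjusted regression with an assumed follow-up mean of 6, SD 5 and correlation 0.25 (300 runs per setting) gave mean differences of +1.00 and −0.34 at 10% missing and +3.61 and +2.41 at 20%, for true benefits of 1.5 and 3. These agree with the formula.

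**What a tipping-point analysis would show instead.** Shift only the missing intervention scores by δ, which moves the difference by mδ, and take the standard error as unchanged (an approximation).

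- 20% dropout: SE = 7.02 × √(2/461) ≈ 0.46; half-width 1.96 × 0.46 ≈ 0.91; δ = (1.5 − 0.91) / 0.20 ≈ 3 points.
- 10% dropout: SE = 7.02 × √(2/519) ≈ 0.44; half-width ≈ 0.85; δ = (1.5 − 0.85) / 0.10 ≈ 6.5 points.

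A reader can judge values such as these.

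**The case against.** The best defence is that a best/worst-case calculation is a legitimate outer bound. Surviving it is strong evidence, and at low missingness (below 5.9% for the target effect) it can be survived in sign. The analysis is also conditional and supportive, so the primary estimate does not depend on it. All of that stands. It does not justify presenting the bound as a threshold test of stability.

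Four stronger readings are tempting, and the documents do not support them:

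- *The rule reverses any plausible benefit.* Within the differences the protocol names, this holds at 20% missing. At the anticipated 10%, a 3-point benefit keeps its sign at −0.3, although it is far from significant.
- *This is the trial's only missing-data sensitivity analysis.* Section 8.3.1 calls the text a brief outline, and the SAP is not shown. Further analyses, and the trigger for running this one, may be set there.
- *The analysis handles missingness through baseline PHQ-8 alone.* Section 5.1.1 allows adjustment for stratification variables, and Section 8.3.4 adds supportive models with the minimisation variables.
- *The trial will declare a sound result unstable.* Section 8.3.4 states no pass/fail rule, so a sign change need not be read that way. The risk is that readers take it so, given the stated purpose.

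**Conclusion.** The point holds in a limited form. Section 8.3.4 offers one extreme bound as a threshold analysis. At the protocol's own dropout figures it turns the 1.5-point target benefit into apparent harm: 1.05 points at 10% and 3.6 points at 20%. At 20% it also reverses the usual important difference of 3. The result is driven mainly by the dropout rate and the width of the scale, and no threshold is located, so the rule does not serve its stated purpose.

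The figures rest on three assumptions: a 24-point range inferred from the item count; analysis on the untransformed score, although Section 5.1.1 permits transformation; and equal missingness by arm. If dropout fell almost wholly in the control arm, the shift would depend on the unknown control mean and could be smaller. The primary analysis itself is not affected.

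**What to change.** Replace the rule in Section 8.3.4 with a delta-adjusted tipping-point analysis of the primary outcome, to be run whatever the dropout:

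1. Impute missing 6-month PHQ-8 scores under missing at random.
2. Shift the imputed scores separately in each arm, over a range wide enough to reach the point where the conclusion changes. At 10% dropout a range that stops at 6 points would just miss it for the target effect, so the range must go further.
3. Report the shifts at which the conclusion changes. If the primary result is null, report the estimates and intervals across the range instead.
4. Keep the best/worst case, if wanted, only as an outer bound and label it so.

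The cost is a little more analysis code. No extra data, visits or participants are needed.
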